#### 7.4 Missing Data

Handling of missing data will include descriptive analysis of missing data patterns followed by the analysis of reasons for missingness as a nominal response using multinomial logistic regression. The focus of the descriptive analysis will be to assess associations between treatment assignment and data missingness. We will compare analyses conducted with missing data imputation and missing data exclusion under a missing-at-random assumption. These sensitivity analyses will assess the degree to which mechanism underlying the data missingness affects the findings of the study. Missing data imputation will be conducted using predictive-matching algorithms. We do not expect more than 15% of data to be missing. If the rate of data missingness is greater than 15%, multiple imputation approaches will be utilized in the primary analyses.

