Missing data. With high-dimensional phenotyping and the longitudinal character of the study missing data will be inevitable. Handling of missing data will include descriptive analysis of missing data patterns followed by the analysis of reasons for missingness as a nominal response using multinomial logistic regression. Sensitivity analyses will include missing data imputation by predictive-matching algorithms and missing data exclusion under a missing-at-random assumption. We do not expect more than 15% of missing data. If this assumption is not confirmed, multiple imputation approaches will be utilized.

Safety monitoring. Even though no serious side effects are expected from the treatments, in addition to the safeguards in the SMART trial of the Research Project, the Core will monitor safety periodically with 3 interim analyses and one final analysis, using the Fleming design (Fleming, T.R. (1982) One-Sample Multiple Testing Procedure for Phase II Clinical Trials, *Biometrics* 38, 143-151). The analysis will occur after each consecutive recruitment group of another 100 patients has completed their treatments (400 planned patients total under active treatments after drop-out).

Although it is highly unlikely that there will be extensive adverse events related to the study treatment that is any grade 2 or higher because these are all commonly used treatments for cLBP, we have established

an alarm procedure. The alarm procedure is designed to give early warning if the rate of any related AEs, grade 2 or reaches 15% or above. We will consider an alarm when more than 22, 32, 42, and 52 patients show adverse events and classify as related events and are a grade 2 or higher at the 3 interim tests and the final analysis, respectively. Events that may require the study to be discontinued or participant to be withdrawn from the study are described in Section 22.

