### 8.3 Protocol Deviations

An accidental or unintentional change to, or non-compliance with the research protocol that does not increase risk or decrease benefit or; does not have a significant effect on the subject's rights, safety, or welfare; and/or on the integrity of the data. Deviations may result from the action of the subject, researcher, or research staff's departure from the IRB approved research protocol without prior IRB approval for the variation. Missing data are part of protocol deviations and may lead to exclusion from the per-protocol analysis population.

Participant-specific protocol deviations will be assessed for their potential relationship to the treatment effects or the course of the disease by a medical expert. Since deviations because of safety will generally result in incomplete data on the subject, their consequences will be handled in the analysis as potentially informative missing data (see Section 8.4). Due to the difficulty of accurate determination of the relationship between protocol deviations and the treatment efficacy and the disease dynamics, several versions of the primary and secondary analysis will be undertaken:

1. Exclusion of the violators from the analysis population under the missing at random assumption.
2. If missing data fraction exceeds 15%, multiple imputation of the violator's unobserved responses using predictive matching algorithms, including the per-protocol analysis of the resultant imputed population(s).
3. With yes/no responses that have the meaning of success or failure where mixed logistic models are used per protocol, violator's responses will be classified as failures for the conservative analysis.
4. Analytic methods (2,3) applied only to violators classified as treatment or disease-related as defined by medical experts.

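### The SAP 7.4 sensitivity analysis cannot show the effect of informative dropout, because both methods compared assume missing at random and nothing planned for the continuous primary endpoint departs from that

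*SAP*

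**What the plan says.** SAP 7.4 begins with descriptive work: patterns of missing data, a multinomial model of the reasons, and the association of missingness with treatment assignment. It then says "We will compare analyses conducted with missing data imputation and missing data exclusion under a missing-at-random assumption". The stated purpose follows: "These sensitivity analyses will assess the degree to which mechanism underlying the data missingness affects the findings of the study". The imputation method is given in one line, "Missing data imputation will be conducted using predictive-matching algorithms", with no list of imputation variables.

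The expectation is "We do not expect more than 15% of data to be missing". Above that level, "multiple imputation approaches will be utilized in the primary analyses", with no stated departure from MAR. Protocol 18.1.5 plans the same pair: "Sensitivity analyses will include missing data imputation by predictive-matching algorithms and missing data exclusion under a missing-at-random assumption".

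SAP 8.3 turns to deviations made for safety reasons and says "their consequences will be handled in the analysis as potentially informative missing data (see Section 8.4". SAP 8.4 is the list of demographic and baseline variables. Other SAP cross-references run one section too high (7.2.2 cites 9.5 for compliance, which is in 8.5), so 7.4 is presumably meant.

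SAP 8.3 also says "Missing data are part of protocol deviations and may lead to exclusion from the per-protocol analysis population". Its list of alternative analyses holds exclusion under MAR, multiple imputation by predictive matching when more than 15% is missing, violators counted as failures where the response is yes/no, and the last two restricted to treatment- or disease-related violators.

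The primary endpoint (SAP 4.3) is continuous: change in PROMIS pain interference from T2 to T3.

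**The concern.** A comparison of two MAR analyses cannot show what happens when MAR fails, yet the SAP gives that as its purpose. The setting makes failure plausible. Patients and staff are unblinded, and the four treatments differ in burden and tolerability (group sessions, clinic physical therapy, daily self-acupressure, a drug with listed side effects). Reasons for leaving may therefore differ by arm and by phenotype.

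The targets are treatment-by-phenotype interactions, tested at |W| >= 2 (SAP 9.1.1) with no formal multiplicity control (SAP 7.5). An interaction produced by dropout could pass the planned check and be carried forward as a predictor of response.

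**Working it through.** **1. The plan's own figures.** The 15% has no derivation to reproduce. The power statement in SAP 6.1 sets the scale for the simulation. By Fisher z, power = Phi(atanh(r) x sqrt(n-3) - 1.96). With r = 0.28 and n = 102 this is Phi(2.862 - 1.960) = 81.7%, which agrees with the stated 80% or more. With residual SD 6 (assumed), r = 0.28 corresponds to an interaction of 1.75 points per SD of phenotype, since 1.75/sqrt(1.75^2 + 6^2) = 0.28.

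**2. Why the two methods share the bias.** For arm a and phenotype z, let pi(a,z) be the probability that T3 is missing and delta(a,z) the mean of the missing outcomes minus the mean of the observed ones. Then

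true mean = observed mean + pi(a,z) x delta(a,z).

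Exclusion models the observed mean. Predictive matching on the same variables fills gaps with observed donors who have similar predictions, so it reproduces the observed mean. Neither estimates delta. The interaction is biased whenever pi x delta changes with z in one arm more than in the others.

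**3. Size when imputation uses the model variables.** All simulations have 4 arms of 102 and T3 only, with exclusion compared against predictive mean matching (5 donors, 5 imputations). The true interaction is zero. Patients with poor outcomes leave only among high-phenotype patients of one arm. Outcome spread and dropout strength are assumptions; neither document gives them.

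| Setting | Exclusion | Imputation | Declared, \|W\| >= 2 |
|---|---|---|---|
| 13% missing, 21-23% in the arm, outcome SD 8, 800 trials | -0.80 | -0.79 | 19% |
| 13% missing, 21-22% in the arm, other assumed settings, 800 trials | -0.85 | -0.85 | 12% |
| 15% missing, residual SD 6, 500 trials | -0.66 | -0.66 | 17.2% exclusion, 22.0% single imputation |

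In the last row the complete data give 0.03 and 5.4%, so the bias is -0.66 - 0.03 = -0.69. Part of the 22.0% comes from single imputation understating the error: with data missing completely at random it rejects 8.4%, against 4.2% for exclusion. In the first two rows the methods agree within half a standard error in 96% and about 99% of trials. With the last row's settings, the bias is about -0.55 at 10% missing and -0.86 at 20%.

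A second mechanism lets dropout depend on the T3 score in every arm, with a true interaction of -1.75. Complete data give -1.72, exclusion -1.49 and imputation -1.46. Under missing completely at random and under MAR, both methods are unbiased, with a mean gap of about 0.02 or less.

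**4. Size when imputation also uses mid-treatment scores.** PROMIS pain interference is collected at weeks 8, 10 and 12, during the first treatment (weeks 7-14; SAP Table 1, Protocol 12.1). An auxiliary score with the stated correlation with the T3 residual was added to the imputation only, at 15% missing.

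| Correlation | Share of exclusion bias shown by the gap: one-arm case | All-arm case |
|---|---|---|
| 0.5 | 24% | 7% |
| 0.7 | 46% | 30% |
| 0.85 | 71% | 55% |

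The rest stays hidden in both analyses.

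**5. Does a delta analysis respond?** Adding 8 points to imputed values in the one-arm case moves the estimate from -0.66 to 0.12 (complete data 0.03). Adding 6 points in the all-arm case moves it from about -1.48 to -1.71 (complete data -1.72). These deltas were chosen to suit the simulated mechanisms. They show that the analysis reacts to the mechanism and are not recommended values.

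**The case against.** **The two methods need not agree.** A reader might infer that the planned comparison will always report that the mechanism is unimportant. The documents do not support that. SAP 7.4 names no imputation variables, and the mid-treatment scores are available. If they are used, the methods can diverge and reveal part of the bias (step 4). This stands: the comparison can mislead, but it need not.

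**Other checks are planned.** Missingness is examined by arm (SAP 7.4 and 8) and dropout reasons are recorded where possible (SAP 8.1). With 13% missing overall and 22% in one arm, the others have (4 x 13 - 22)/3 = 10%. A four-arm chi-square then has noncentrality 102 x (0.09^2 + 3 x 0.03^2)/(0.13 x 0.87) = 9.74 and flags the imbalance in about 75% of trials. So a reader of the results would often see a warning. It shows that dropout differed, not what it did to the estimate. Protocol 22.2 also asks patients who stop an intervention to attend remaining visits, which should reduce missing outcomes but leaves the assumption unchanged.

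**One planned analysis does depart from MAR.** It would be wrong to infer that none does. SAP 8.3 counts violators as failures for yes/no responses, and Protocol 18.1.5 plans 30% and 50% improvement as binary robustness forms, so under the protocol this could reach a dichotomised pain response. SAP Section 9 specifies no such analysis, and the rule does not apply to the continuous endpoint.

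**The simulated sizes are conditional.** This stands. A larger figure is available for a simple arm contrast (bias about -1.43, declared in 34% of trials), but the primary tests are interactions, so it is not the relevant size.

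**Conclusion.** The point holds in limited form. SAP 7.4 assigns the imputation-versus-exclusion comparison a purpose it cannot serve for dropout driven by unseen outcomes. SAP 8.3 anticipates informative missingness without supplying a method for the continuous primary endpoint.

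Under the assumed one-arm mechanism with about 13-15% missing, within or at the plan's own expectation, a null interaction is biased by about -0.7 to -0.85 points under both methods and declared in about 12-22% of trials. This rests on imputation from the model variables, assumed spread and dropout strength, and a T3-only model rather than the joint T3/T4 model. The real bias cannot be known from the documents and may be small. That is the reason for a tipping-point analysis.

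The MAR pair keeps some value. Exclusion with working-independence GEE is valid when missingness depends only on model covariates, so a gap between the methods indicates dependence on variables outside the model. It should be fixed before analysis, but it does not undermine the design.

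**What to change.** 1. **Keep the MAR pair and relabel it** in SAP 7.4 as a check of dependence on auxiliary variables outside the analysis model. Name the imputation variables, including the week 8, 10 and 12 pain interference scores.
2. **Add a delta-adjusted multiple imputation** of the PROMIS pain interference outcomes in the primary model: T3, and T4 if the joint model is kept.
3. **Apply delta first in all arms.** Then, for each of the eight hypothesised interactions, apply it in the arm concerned and let it vary with the modifier: by category for sex, and for continuous scores toward each end in turn, or at least toward the predicted-responder end. That end is the low one for self-efficacy and the Experiences Questionnaire (Protocol 18.1.1 and 18.1.2), so a rule based only on high scorers would miss it.
4. **Report the delta at which each conclusion changes.** State the range as an assumption. For example, 0 to 8 points in steps of 2 reaches 0.8 of the PROMIS population SD of 10. The documents give no basis for a particular range.
5. **Correct the 8.3 cross-reference** so that it points to this analysis.

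Cost: with four non-zero deltas, 4 x (1 + 8) = 36 settings, or 4 x (1 + 16) = 68 with both directions (both categories for sex), each multiply imputed. The runs can be scripted, and the tipping points fit in one table. There is more to report, but no new data or visits.

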Handling protocol deviations. Participant-specific protocol deviations will be assessed for their potential relationship to the treatment effects or the course of the disease by a medical expert. Since deviations because of safety will generally result in incomplete data on the subject, their consequences will be handled in the analysis as potentially informative missing data (as described above). Because of the difficulty of accurate determination of the relationship between protocol deviations and the treatment efficacy and the disease dynamics, several versions of the primary and secondary analysis will be undertaken:

Exclusion of the violators from the analysis population under the missing at random assumption.

1. Single (if, as expected, missing data fraction does not exceed 15%) or multiple imputation of the violator's unobserved responses using predictive matching algorithms, including the per-protocol analysis of the resultant imputed population(s).
2. With yes/no responses that have the meaning of success or failure where mixed logistic models are used per protocol, violator's responses will be classified as failures for the conservative analysis.
3. Analytic methods (2,3) applied only to violators classified as treatment or disease-related as defined by medical experts.

Power for explaining treatment effects. Consider a regression model correlating within-patient improvement due to one of the 4 main treatments with a phenotypic variable. Using a two-sided test for correlation at 5% significance level we conclude that we will have the power of at least 86% to detect correlation of 0.3 or higher, conservatively assuming the model is applied to one randomized treatment segment with 100 patients. This corresponds to first phase or second phase treatment in one of the 4 treatment groups, and a model based on the light phenotyping patient group of 400 total. Similar analysis for the smaller subgroup based on 40 patients with available deep phenotyping for a specific treatment and segment shows that correlation of 0.43 or higher will be detectable with 81% power. This is well within reach as evidenced by available literature on the association between treatment effects and phenotype variables. For example, mindfulness and pain responses showed correlations of 0.43-0.51 in prior reported studies. Our previous studies of the association between pain centralization and analgesic responses in knee OA showed similar or higher correlations.

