### 6.1 Power for explaining treatment effects

Consider a regression model for correlating within-patient improvement (primary: change in PROMIS Pain Interference; secondary: change in PEG, PGIC; many others as exploratory, see below for details) due to one of the 4 main treatments with a phenotypic variable. Using a two-sided test for correlation at 5% significance level we conclude that we will have the power of at least 80% to detect correlations of 0.28 or higher, conservatively assuming the model is applied to one randomized treatment segment with 102 patients. This corresponds to first phase or second phase treatment in one of the 4 treatment groups, and a model based on the light phenotyping target patient group of 408 total. Similar analysis for the smaller subgroup based on 40 patients with available deep phenotyping for a specific treatment and segment shows that correlation of 0.42 or higher will be detectable with 80% power. This is well within reach as evidenced by available literature on the association between treatment effects and phenotype variables. For example, mindfulness and pain responses showed correlations of 0.43-0.51 in prior reported studies. Our previous studies of the association between pain centralization and analgesic responses in knee osteoarthritis showed similar or higher correlations.

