We will fit the model for all repeated measures ( $Y_{3i}, Y_{4i}$ ) using generalized estimating equations (GEE) with a working independence covariance matrix through the R package *gee*. We will use robust standard errors for variance estimation to account for the use of repeated measures. Prior to conducting inference, we will assess the functional forms of the predictors and the validity of the assumptions required for joint stage modeling, especially the assumption of constant interaction effects across treatment stages. If the assumptions for joint modeling are violated, we will conduct the primary analysis with stage 1 data only. For inference, we additionally assume  $Y_{3i}, Y_{4i}$  follow a multivariate normal distribution.

The clinical objective of Aim 1 is to show that patient responsiveness to treatment depends on their

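### Multiple imputation is reserved for more than 15% missing data, which leaves the expected case to single imputation for protocol violators and an unnamed primary method

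*SAP*

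**What the plan says.** Both documents tie the missing-data method to a threshold. SAP 7.4: "If the rate of data missingness is greater than 15%, multiple imputation approaches will be utilized in the primary analyses". The same paragraph says that no more than 15% is expected. The missing-data paragraph of Protocol 18.1.5 and the protocol-deviation list in SAP 8.3 use the same trigger.

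Below the threshold the texts differ:

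- Protocol 18.1.5, on handling protocol deviations, gives this option for what violators did not report: "Single (if, as expected, missing data fraction does not exceed 15%) or multiple imputation", by predictive matching.
- The matching list in SAP 8.3 mentions only multiple imputation above 15% and is silent below it.
- SAP 7.4 says that an imputed analysis (predictive matching, number of imputations not stated) will be compared with "missing data exclusion under a missing-at-random assumption", and calls the comparison sensitivity analyses. It does not name the primary method at or below 15%, and it does not define the denominator of the rate.

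The primary model in SAP 9.1.1 is a GEE with a "working independence covariance matrix" and robust standard errors. It adjusts for sex, age, BMI, race, education, the T2 score and the hypothesized modifiers. PROMIS Pain Interference is also collected at the mini-assessments (SAP Table 1), including weeks 8, 10 and 12 during the first treatment (Protocol 12.1). Those scores are not in the model.

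**The concern.** A method that carries the uncertainty of missing values is used only where the plan does not expect to be. In the expected range there are two weaknesses.

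First, a single imputed data set analysed as if fully observed understates the standard error at any missing fraction; 15% is not a level below which this is harmless. SAP 7.5 reports results by confidence intervals without multiplicity control, so interval width is what readers will rely on.

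Second, a GEE with working independence and no stated missing-data method uses the rows that are complete. That is valid when missingness depends only on covariates in a correctly specified model. It is not valid in general under missing at random when dropout depends on something observed but left out, such as pain at week 12.

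**Working it through.** **1. The plan's own figure.** The 15% trigger is a rule, so the only figure to reproduce is the power in SAP 6.1. Inputs from that section: a two-sided 5% test, n = 102 in one arm and period, and the stated "power of at least 80% to detect correlations of 0.28 or higher". Fisher z: power = Φ(atanh(r)·√(n−3) − 1.96) = Φ(0.2877 × 9.950 − 1.96) = Φ(0.902) = 81.7%. The figure reproduces.

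If 102 counts patients randomized (SAP 5.5) and not patients available for analysis (SAP 6), a 15% loss leaves 86 complete cases: Φ(0.2877 × 9.110 − 1.96) = 74.6%.

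**2. Single imputation, closed form.** Let m be the fraction missing, with one random draw per missing value and no auxiliary information. The naive variance is σ²/n. The true variance is (σ²/n) × [1/(1−m) + m]: the first term is estimation from the observed fraction, the second is noise in the draws. The ratio of naive to true SE is therefore 1/√[1/(1−m) + m]. At m = 0.15: 1/√(1.176 + 0.15) = 1/√1.326 = 0.868. Coverage is that of a nominal 95% interval. Error is 2·[1 − Φ(2 × ratio)], using the SAP 9.1.1 rule of rejecting at |W| ≥ 2 (nominal 4.6%).

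| m | SE ratio | 95% coverage | error |
|---|---|---|---|
| 5% | 0.952 | 93.8% | 5.7% |
| 10% | 0.909 | 92.5% | 6.9% |
| 15% | 0.868 | 91.1% | 8.3% |

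**3. Single imputation, simulated.** Setting: a T3-only model with 408 patients, four arms, a baseline score, one modifier and one interaction, robust SE, true effects zero, 1,500 runs. Monte Carlo error on a 5% rate is √(0.05 × 0.95/1500) = 0.6 points. Results for the interaction at 15% missing, as SE ratio / rejection:

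| missingness depends on | no data missing | complete cases | single imputation | 20 imputations |
|---|---|---|---|---|
| nothing | 1.017 / 4.8% | 1.008 / 4.5% | 0.931 / 7.3% | 1.015 / 5.0% |
| model covariates | 0.978 / 5.3% | 0.981 / 5.1% | 0.862 / 9.1% | 0.986 / 4.3% |
| interim score | 0.981 / 5.4% | 0.976 / 6.1% | 0.884 / 7.7% | 0.986 / 5.4% |

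At 5% missing the single-imputation SE ratio is about 0.95, with rejection 5.3–6.7%. A second simulation (five donors, random loss, 2,000 runs) gave ratios of 0.93, 0.875 and 0.86 at 5%, 10% and 15%, with error 6.9%, 8.4% and 8.8%. A third, with eight interactions, gave an SE 10–17% too small at 15% and error 7.6–10.1%, where complete data already gave 5.4–6.0%.

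**4. Complete cases.**

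- *Missingness at random or on model covariates:* bias about zero.
- *Dropout driven by the interim score in opposite directions in two arms (assumed, strong), true effects zero:* arm-contrast bias −0.07, −0.13 and −0.18 SD at 5%, 10% and 15% missing, with rejection 7.9%, 17.4% and 29.5%. The interaction stays unbiased (at most 0.003).
- *True interaction of 0.29 SD, dropout in one arm driven by week-12 pain:* 0.29 is an assumption. It is the slope in residual SDs implied by r = 0.28 in one arm and none elsewhere: 0.28/√(1 − 0.28²) = 0.28/0.96 = 0.29. With a logit slope of 1.5, residual correlation 0.7 and about 14% missing overall, bias is −0.035 SD (0.035/0.29 = 12%). It is −0.07 SD if the modifier also has a main effect of 0.3. With 13–14% missing in every arm it is 0.018–0.027 SD toward zero, against an SE of 0.12. If week-12 pain does not carry the interaction, it is 0.002–0.003 SD.

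**5. Multiple imputation.** With 20 imputations and the interim score in the imputation model, rejection is 4.0–5.9% and the SE ratio 0.975–1.016 across 5–15% missing. The arm-contrast bias at 15% falls from −0.18 to −0.01 SD. In the true-interaction setting, regression-based imputation by arm with the week-12 score left bias of 0.001 SD or less and error of 4–6%. Predictive matching within arm removed only about a third of the bias, because each arm offers few donors.

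**The case against.** The SAP never uses the word single. That option is written only in the protocol, for protocol violators. A reader might infer that below 15% the primary analysis is single imputation, or that it is declared to be complete-case; the documents say neither. Complete rows are what the GEE would use by default, not a stated choice.

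A reader might also infer that the imputation ignores the two-weekly scores. No list of imputation predictors is given, and for multiple imputation SAP 7.4 cites a strategy written for sequential multiple-assignment trials. So this is unspecified, not excluded.

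The primary test is the interaction. With no true interaction, complete cases showed no bias in it and no rejection beyond simulation error, even under strong dropout. The claim that the planned comparison will produce false positives is therefore too strong: single imputation raises the error rate by a few points, and complete cases were not shown to raise it for the interaction.

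The plan also has protections. Follow-up continues after an intervention is stopped (Protocol 22.2), each missed visit prompts three contact attempts (Protocol 15 and 22.3), and missingness is compared by arm (SAP 7.4 and 8).

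These points limit the size of the problem. They leave standing the threshold in both documents, the single-imputation option in the protocol and the unnamed primary method in the range the plan expects.

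**Conclusion.** The point holds as a stated rule that withholds multiple imputation in the expected range. The understated SE under single imputation does not depend on a dropout mechanism; its size at 15% missing varies between settings over the ranges in the check.

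The complete-case part is conditional. It needs dropout that depends on interim pain, differs between arms and is not explained by model covariates. For the interaction it also needs a true effect, which is then attenuated. The roughly 0.02–0.07 SD rests on assumed strong mechanisms, and the documents give nothing from which to judge how likely these are. A reader might conclude that the primary interaction test is invalid; neither the documents nor the calculations support that. All simulations used T3 only, not the joint T3/T4 model.

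**What to change.** In SAP 7.4, name multiple imputation as the primary method at any level of missing data and state the number of imputations. Use a regression-based imputation model that allows treatment-by-modifier interactions, or impute by arm, and include the two-weekly PROMIS Pain Interference scores as auxiliary variables. Predictive matching within arm is not an adequate substitute at these arm sizes.

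Delete the 15% switch in SAP 7.4, SAP 8.3 and Protocol 18.1.5, which also removes the need to define the rate's denominator. Delete the single-imputation option in the deviation paragraph of Protocol 18.1.5. Keep complete cases as a sensitivity analysis.

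The cost is wording in both documents, a little more programming, and slightly wider intervals than single imputation would give. No new data are needed.
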